	Repeat LFTs ^b as soon as possible, preferably within 48-72 hours from awareness of the abnormal results; monitor LFTs ^b at least weekly, until resolved to baseline or stabilization over 4 weeks.	
Combined ^c elevations of AST or ALT and total biliru	ıbin	
For participants with normal baseline ALT and AST and total bilirubin value:	Mandatory: Interrupt study treatment and adjudicate for DILI:	
AST or ALT >3.0 × ULN combined with total bilirubin > 2.0 × ULN without evidence of cholestasis ^d and Gilbert's syndrome For participants with elevated baseline AST or	Repeat as soon as possible, preferably within 48 hours from awareness of the abnormal results, monitor LFTs ^b at least weekly, or as clinically indicated, until AST, ALT, and total bilirubin have resolved ≤ Grade 1 or to baseline.	
ALT or total bilirubin value: AST or ALT > 3 × baseline OR > 8.0 × ULN.	If causality assessment indicates that DILI is	
whichever is lower, combined with total bilirubin > 2 ×	confirmed: Permanently discontinue study treatment.	
baseline AND > 2.0 × ULN Note: For participants with Gilbert's syndrome, at least 2-fold increase in direct bilirubin.	If not DILI: Treat the identified cause according to institutional guidelines. Once resolved to ≤ Grade 1 or to baseline, may reintroduce study treatment at 1 lower dose level if clinically indicated, following discussion with Novartis medical monitor.	
	Refer to Section 6.5.3.1 for further details on the follow up of potential drug-induced liver injury (DILI) cases.	
Investigation (metabolic)		
amylase and/or lipase elevation		
Grade 1 (> ULN - 1.5 × ULN)	Recommendation: Maintain study treatment and dose level.	
Grade 2 (> 1.5 - 2.0 × ULN)	Recommendation: Maintain study treatment and dose level.	

Grade 3 (> 2.0 - 5.0 × ULN) with signs or symptoms; > 5.0 × ULN and asymptomatic.**	Recommendation: Interrupt study treatment until resolved to Grade ≤ 1 or baseline, then:	
	If resolved in ≤ 7 days, resume study treatment at the same dose level.	
	If resolved in > 7 days, reduce 1 dose level.	
Grade 4 (> 5.0 × ULN with signs or symptoms)**	Mandatory: Permanently discontinue study treatment.	
Cardiac Investigations		
Left Ventricular Ejection Fraction (LVEF)		
LVEF < 40%	Mandatory: Interrupt study treatment, obtain consultation with cardiologist and repeat cardiac imaging after 3 weeks. If improved to > 45%, restart study treatment at the same dose. If not improved to >45%, permanently discontinue study treatment.	
LVEF 40%- ≤45% and decrease is ≥ 10%-points below baseline	Mandatory: Interrupt study treatment, obtain consultation with cardiologist and repeat cardiac imaging after 3 weeks. If LVEF has recovered to within 10%-point below baseline, restart study treatment at the same dose. If LVEF has not recovered to within 10%-points below	
	baseline, permanently discontinue study treatment.	
LVEF 40% to ≤45% and decrease is < 10%-points below baseline	Mandatory: Continue treatment. Obtain consultation with a cardiologist and repeat LVEF assessment within 3 weeks. If LVEF is stable/improving, no further action is needed. If there is a further decrease in LVEF, please follow the above guidance.	
ECG QTc-Interval prolonged		
Grade 1 and 2	Recommendation: Maintain treatment and dose level.	
Grade 3	Mandatory: Interrupt study treatment. Upon resolution to Grade ≤ 1 or baseline or < 30 msec difference from baseline (QTc), reduce 1 dose level. May resume JDQ443 treatment without dose modification after discussion with the Novartis Medical Monitor if other contributing factors have been identified. Baseline ECG refers to the ECG(s) collected at screening.	
Grade 4	Mandatory: Permanently discontinue study treatment.	
Vascular disorders		
Hypertension		
Grade 1 and 2	Recommendation: Maintain study treatment and dose level.	
Grade 3	Recommendation: Interrupt study treatment until resolved to ≤ Grade 1, then reduce 1 dose level.	
Grade 4	Mandatory: Permanently discontinue study treatment.	
Gastrointestinal		
Diarrhea***		
Grade 1	Recommendation: Maintain study treatment and dose level. Treat the patient per institutional practice.	
Grade 2	Recommendation: Interrupt study treatment until resolved to ≤ grade 1, treat the patient per institutional practice, then reintroduce study treatment at the same dose level.	

	If diarrhea returns as ≥ grade 2, then interrupt study treatment until resolved to ≤ grade 1 and reduce 1 dose level.	
Grade 3	Recommendation: Interrupt study treatment until resolved to ≤ Grade 1, treat the patient per institutional practice, then:	
	If resolved in ≤ 48 hours, maintain dose level.	
	If resolved in > 48 hours despite the use of optimal anti-diarrhea therapy, reduce 1 dose level.	
Grade 4	Mandatory: Permanently discontinue study treatment.	
Nausea & Vomiting		
Grade 1 and 2	Recommendation: Maintain study treatment and dose level, provide anti-emetic treatment per institutional practice.	

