6.5 Dose modification

6.5.1 Dose modification guidelines

For participants who do not tolerate the protocol-specified dosing schedule, dose interruptions, and/or reductions are either recommended or mandated in order to allow participants to continue the study treatment.

These dose modifications for JDQ443 are summarized in Table 6-3 and Table 6-4. Deviations to mandatory dose interruptions and/or reductions are not allowed. Permanent discontinuation from study treatment is mandatory for specific events indicated as such in Table 6-3 and Table 6-4.

Dose reductions are allowed for JDQ443 and should follow the dose reduction steps described in Table 6-3 and Table 6-4. For each participant, a maximum of two consecutive dose level reductions is allowed after which the participant must be discontinued. Dose reductions of JDQ443 below 100 mg QD. are not permitted.

Dose re/escalation of JDQ443 to previous dose level is allowed only once, and if no AE leading to dose modification is observed after at least 1 cycle (21 days) of study treatment at the reduced dose.

For toxicities related to study treatment that resolve within 7 days of event onset, treatment may be resumed at the same or a lower dose level at the Investigator's discretion, except for toxicities that require permanent treatment discontinuation (Table 6-3 and Table 6-4).

For toxicities related to study treatment that result in dose interruptions of more than 7 but not more than 21 days, study treatment may be resumed but only at a lower dose level. If the participant is already at the lowest dose level, participant might continue receiving treatment at the same dose level if participant is deriving clinical benefit from JDQ443. In such situation, the Investigator must discuss and receive approval from Novartis Medical Monitor or designee prior to continuing JDQ443 and rationale should be captured in the source document.

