If the participant requires a dose interruption of more than 21 days from the intended day of the next scheduled dose, then the participant must be discontinued from the study treatment. Exceptions to this criterion may be considered if the participant is deriving clinical benefit from the treatment. The Investigator must discuss and receive approval from Novartis Global Medical Director or designee prior to continuing study treatment in this situation and rationale should be captured in the source documents. If study treatment is reintroduced after an interruption of more than 21 days caused by an adverse event, study treatment can only be reintroduced at a lower dose level. If study treatment is reintroduced after an interruption of more than 21 days that was not caused by an adverse event, study treatment may be reintroduced without dose reduction.

All dose changes must be recorded on the appropriate eCRF.

Criteria for dose reduction / interruption and re-initiation of JDQ443 treatment for adverse drug reactions. Table 6-3

	reactions.
Dose modifications for JDQ443	
Worst toxicity	
CTCAE Grade ^a (value) during a cycle of therapy	
Investigations (Hematologic)	
Neutropenia (ANC)	
Grade 1 (ANC < lower limit of normal (LLN) - 1500/mm³)	Recommendation: Maintain study treatment and dose level.
Grade 2 (ANC < 1500 - 1000/mm ³)	Recommendation: Maintain study treatment and dose level.
Grade 3 (ANC < 1000 - 500/mm ³)	Recommendation: Interrupt study treatment until resolved to ≤ Grade 2, then:
	If resolved in ≤ 7 days, maintain dose level.
	If resolved in > 7 days, reduce 1 dose level.
Grade 4 (ANC < 500/mm³)	Mandatory: Interrupt study treatment until resolved to ≤ Grade 2, then reduce 1 dose level.
Thrombocytopenia	
Grade 1 (PLT < LLN - 75,000/mm ³)	Recommendation: Maintain study treatment and dose level.
Grade 2 (PLT < 75,000 - 50,000/mm ³)	Recommendation: Maintain study treatment and dose level.
Grade 3 (PLT < 50,000 - 25,000/mm ³)	Recommendation: Interrupt study treatment until resolved to ≤ Grade 2, then:
	If resolved in ≤ 7 days, maintain dose level.
	If resolved in > 7 days, reduce 1 dose level.
	Mandatory: For Grade 3 thrombocytopenia associated with major bleeding, permanently discontinue study treatment.
Grade 4 (PLT < 25,000/mm³)	Mandatory: Interrupt study treatment until resolved to ≤ Grade 2, then reduce 1 dose level.
	Mandatory: For Grade 4 thrombocytopenia associated with major bleeding, permanently discontinue study treatment.

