Febrile neutropenia (ANC < 1.0×10^9 /L, with a single temperature of >38.3 degrees C [101 degrees F] or a sustained temperature of \geq 38 degrees C [100.4 degrees F] for more than one hour)	Mandatory: Interrupt study treatment until resolved, then reduce 1 dose level.
Anaemia	
Grade 1 (Hemoglobin [Hgb] < LLN - 10.0 g/dL; < LLN - 6.2 mmol/L; < LLN - 100 g/L)	Recommendation: Maintain study treatment and dose level.
Grade 2 (Hgb < 10.0 - 8.0 g/dL; < 6.2 - 4.9 mmol/L; < 100 - 80 g/L)	Recommendation: Maintain study treatment and dose level.
Grade 3 (Hgb < 8.0 g/dL; < 4.9 mmol/L; < 80 g/L; transfusion indicated)	Recommendation: Interrupt study treatment until resolved to ≤ grade 2, then:
	If resolved in ≤ 7 days, resume study treatment at the same dose level;
	If resolved in > 7 days, reduce 1 dose level.
Grade 4 (Life-threatening consequences; urgent intervention indicated)	Mandatory: Interrupt study treatment until resolved to ≤ grade 2, then reduce 1 dose level.

Investigations (Renal)	
Serum creatinine	
Grade 1 (> ULN - 1.5 × ULN)	Recommendation: Maintain study treatment and dose level.
Grade 2 (> 1.5 - 3.0 × ULN)	Recommendation: Interrupt study treatment and manage according to institutional practice.
	Upon resolution to ≤ Grade 1, may reintroduce study treatment at the same dose level if clinically indicated.
Grade 3 (> 3.0 - 6.0 × ULN) and Grade 4 (> 6.0 × ULN)	Mandatory: Permanently discontinue study treatment.
Investigations (Hepatic)	
Isolated total Bilirubin elevation	
Grade 1 (> ULN – 1.5 × ULN)	Recommendation: Maintain study treatment and dose level.
Grade 2 (> 1.5 - 3.0 × ULN)	Recommendation: Interrupt study treatment.
	Repeat LFTs ^b within 48-72 hours, then monitor LFTs at least weekly, until resolved to ≤ 1.5 × ULN or to baseline, then:
	• If resolved in ≤ 7 days, resume study treatment at the same dose level;
	If resolved in > 7 days, reduce 1 dose level.
Grade 3 (> 3.0 - 10.0 × ULN)*	Recommendation: Interrupt study treatment.
	Repeat LFTs ^b within 48-72 hours, then monitor LFTs at least weekly, until resolved to ≤ 1.5 × ULN or to baseline. May reintroduce study treatment at 1 lower dose level if clinically indicated.
Grade 4 (> 10.0 × ULN)*	Mandatory: Permanently discontinue study treatment.
	The participant should be monitored at least weekly (including LFTs ^b), or as clinically indicated, until total bilirubin has resolved to ≤ 1.5 × ULN or to baseline.

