Fatigue/ Asthenia (General disorders and administ	ration site conditions)	
Grade 1 and 2	Recommendation: Maintain study treatment and dose level.	
Grade 3	Recommendation: Interrupt study treatment until resolved to ≤ grade 1, then:	
	If resolved in ≤ 7 days, maintain dose level.	
	If resolved in > 7 days, reduce 1 dose level.	
Ocular (uveitis, eye pain, blurred vision)		
Grade 1	Recommendation: Maintain study treatment and dose level. Ophthalmology consultation is required within 72 hours, except for dry eye.	
Grade 2	Recommendation: Interrupt study treatment.	
	Urgent ophthalmology consultation.	
	Upon resolution to ≤ Grade 1 in < 14 days, may consider reintroducing study treatment without dose reduction after discussion with the Novartis medical Monitor and consultation with ophthalmology.	
	Upon resolution to ≤ Grade 1 in ≥ 14 days, study treatment may be reintroduced at 1 lower dose level after discussion with the Novartis Medical Monitor and consultation with ophthalmology.	
Grade 3 and Grade 4	Mandatory: Permanently discontinue study treatment. Urgent ophthalmology consultation.	
Retinal vein occlusion or Retinal detachment		
Any Grade	Mandatory: Permanently discontinue study treatment. Urgent ophthalmology consultation.	
Other adverse events		
Grade 1 and 2	Recommendation: Maintain study treatment and dose level.	
Grade 3	Recommendation: Interrupt study treatment until resolved to ≤ grade 1, then reduce 1 dose level.	
	Mandatory: Interrupt study treatment for ≥ grade 3 vomiting or grade 3 nausea only if the vomiting or nausea cannot be controlled with optimal anti-emetic therapy (as per local practice).	
Grade 4	Mandatory: Permanently discontinue study treatment.	

^a Common Toxicity Criteria for Adverse Events (CTCAE Version 5.0)

^b Core LFTs consist of ALT, AST, GGT, total bilirubin (fractionated [direct and indirect], if total bilirubin > 2.0 x ULN), and alkaline phosphatase (fractionated [quantification of isoforms], if alkaline phosphatase > 2.0 x ULN)

 $^{^{\}rm c}$ "Combined" defined as total bilirubin increase to the defined threshold concurrently with ALT/AST increase to the defined threshold

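### Table 6-3: above a 55% baseline LVEF, a fall below 40% has an easier restart test than a fall to 40 to ≤45%, and both rows' same-dose restart conflicts with Section 6.5.1

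*Protocol*

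**What the plan says.** Two LVEF rows of Protocol Table 6-3 (Section 6.5.1, Cardiac Investigations) interrupt treatment. Both are labelled mandatory, and both require a cardiology consultation and repeat imaging after 3 weeks.

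- **Row 1, LVEF below 40%:** "repeat cardiac imaging after 3 weeks. If improved to > 45%, restart study treatment at the same dose". If LVEF is not above 45%, treatment stops permanently. Baseline is not mentioned.
- **Row 2, LVEF 40 to ≤45% and at least 10 points below baseline:** "If LVEF has recovered to within 10%-point below baseline, restart study treatment at the same dose". If not, treatment stops permanently.

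The text of Section 6.5.1 sets restart doses by length of interruption:

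- **Treatment-related, up to 21 days:** after interruptions of "more than 7 but not more than 21 days, study treatment may be resumed but only at a lower dose level". There is one exception, which needs clinical benefit and medical monitor approval: "If the participant is already at the lowest dose level, participant might continue receiving treatment at the same dose level".
- **Beyond 21 days:** the participant must discontinue, but "Exceptions to this criterion may be considered if the participant is deriving clinical benefit from the treatment", with sponsor approval. Even then, "after an interruption of more than 21 days caused by an adverse event, study treatment can only be reintroduced at a lower dose level".

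Table 6-4 gives three dose levels: 200 mg b.i.d., 100 mg b.i.d. and 100 mg QD. Going below 100 mg QD is not permitted.

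**The concern.** A dose-modification table should not be more lenient after the worse event. Here, two participants with the same baseline can be told the opposite of what their cardiac findings suggest: the one with the deeper fall and poorer recovery restarts, and the one with the milder fall and better recovery stops for good. Section 2.3 lists cardiac effects among those to be monitored for this drug.

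The restart dose is a second, separate problem. A 3-week wait always exceeds the 7-day window in which Section 6.5.1 allows the same dose at the investigator's discretion. The table row and the section it belongs to then give different doses, and no sentence says which prevails.

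**Working it through.** **Restart tests.** Let B be the baseline LVEF and r the repeat value, both in percent.

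- Row 1 restarts if r > 45.
- Row 2 restarts if r ≥ B − 10. This takes *within 10 points* to include exactly 10, which is an assumption. A strict reading is r > B − 10.
- The thresholds meet where B − 10 = 45, so B = 55, under either reading.

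Whole-point repeat values that restart under row 1 but mean a permanent stop under row 2:

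| Baseline | Row 1 needs | Row 2 needs | Inclusive reading | Strict reading | Points below baseline at r = 46 |
|---|---|---|---|---|---|
| 50% | >45 | ≥40 | none | none | 4 |
| 55% | >45 | ≥45 | none | none | 9 |
| 60% | >45 | ≥50 | 46–49 | 46–50 | 14 |
| 65% | >45 | ≥55 | 46–54 | 46–55 | 19 |
| 70% | >45 | ≥60 | 46–59 | 46–60 | 24 |

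Example at baseline 60%: 39% recovering to 46% restarts at 60 − 46 = 14 points down. 41% recovering to 49% stops at 60 − 49 = 11 points down.

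The SAP gives a cross-check. Section 2.9.4.1 counts an absolute fall of at least 20% as Grade 3. Since 66 − 46 = 20, a participant with a baseline of 66% or more who restarts under row 1 at 46% still meets that criterion.

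**Restart dose.** Three weeks is 3 × 7 = 21 days, so a restart falls either on the 21-day limit or beyond it. Table 6-3 is titled for adverse drug reactions, so the treatment-related rules are the relevant ones.

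| Dose when interrupted | LVEF rows | 6.5.1, >7 to 21 days | 6.5.1, >21 days after an adverse event |
|---|---|---|---|
| 200 mg b.i.d. | same dose | 100 mg b.i.d.: conflict | lower dose only: conflict |
| 100 mg b.i.d. | same dose | 100 mg QD: conflict | lower dose only: conflict |
| 100 mg QD | same dose | same dose, with benefit and approval: no conflict | lower dose only, and none is permitted: conflict |

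That is 2 of 3 levels up to day 21, and 3 of 3 after it.

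**Effect of requiring r > 45 and r ≥ B − 10 in row 1.** For B ≤ 55, r > 45 already implies r > B − 10, so no outcome changes. For B > 55, B − 10 exceeds 45, so row 1 takes on row 2's test and no reversed pair remains.

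**The case against.** **Row 2 may be the outlier.** The table prescribes no LVEF action above 45%, so row 1's threshold matches the point at which an uninterrupted participant would simply continue. After a row 1 restart with a baseline above 55%, any later fall to 40 to ≤45% is necessarily more than 10 points down and meets row 2's stricter test. Both observations are correct, but neither removes the reversed order between the two interruption rows. Relaxing row 2 would also remove it. That is a clinical choice, and tightening row 1 is the more cautious one.

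**The event rows may be meant to govern the dose.** Several rows restate the 7-day rule (neutropenia, anaemia, bilirubin), which suggests that rows without it set their own terms. Grade 2 creatinine reads "Upon resolution to ≤ Grade 1, may reintroduce study treatment at the same dose level if clinically indicated". Grade 2 ocular events read "Upon resolution to ≤ Grade 1 in < 14 days, may consider reintroducing study treatment without dose reduction", which does not fit a governing 7-day rule. This is a fair reading of intent, but the protocol never states it. The ban on deviating from mandatory interruptions and reductions does not literally cover the restart dose.

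**A general precedence sentence looks like the natural remedy.** A reader might infer that, because several rows share the tension, Table 6-3 should simply override Section 6.5.1. The documents do not support going that far. It would remove the required dose reduction after long adverse-event interruptions for creatinine, endocrine, skeletal muscle and other events as well.

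**Exposure is limited.** No heart failure or cardiac dysfunction was seen in the 39 first-in-human patients (Section 2.2.3.3.2). Cardiomyopathy and symptomatic heart failure are excluded (Section 5.2). This stands, and it bears on priority.

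**Conclusion.** Both inconsistencies are real on the text and worth correcting at the next amendment. The first applies only above a 55% baseline. Its size depends on baseline: 46–49% at 60% and 46–54% at 65%, with one more point in each range on the strict reading. The second applies to treatment-related falls.

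Three broader inferences should be avoided.

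- **That the lowest dose escapes the dose conflict.** The lowest-dose exception is written only for interruptions of more than 7 and up to 21 days.
- **That row 1 participants are unprotected.** A cardiologist is consulted, and Section 7.1 obliges the investigator to stop treatment believed harmful. No comparable discretion softens row 2's permanent stop.
- **That the primary result is at risk.** Tumor data after discontinuation count towards best overall response (Protocol 9.3.3, SAP 2.6.3), so exposure is small.

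The number affected cannot be derived: no baseline LVEF distribution is given and the visible eligibility criteria set no minimum. It is probably small. The inversion needs a baseline above 55%, a fall below 40% and only partial recovery, and C2D1 is the only scheduled on-treatment LVEF scan before EOT (Section 8.5.3.1).

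**What to change.** 1. **Row 1:** reword to *If LVEF is >45% and within 10 points of baseline, restart; otherwise permanently discontinue.* State in both rows whether exactly 10 points counts as within.
2. **Restart dose, LVEF rows only:** restart one dose level lower, in line with Section 6.5.1. At 100 mg QD, allow the same dose only with clinical benefit and sponsor approval, including when the repeat image falls just after day 21. Do not add a blanket precedence sentence for all of Table 6-3.
3. **21-day limit:** state that a restart decided on the 3-week image is not by itself a breach of it.

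The cost is rewording the LVEF rows and a short addition to Section 6.5.1. No new assessments are needed. The downside is a few more permanent discontinuations after a fall below 40%, in participants with a baseline above 55% who recover past 45% but stay more than 10 points down. Some other participants would restart at a lower dose than the table now gives.

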	First occurrence: Upon resolution to ≤ Grade 1 in ≤ 7 days, study treatment may be reintroduced at 1 lower dose level. Monitor pulse oximetry daily for 2 weeks and perform chest x-ray 2 weeks after re-initiation, or sooner if clinically indicated.
	If symptoms fail to resolve within 7 days or recur after reintroduction of study treatment, permanently discontinue study treatment.
	Second occurrence: Permanently discontinue study treatment.
Grade 3 and Grade 4	Mandatory: Confirmed ILD
	Permanently discontinue study treatment.
Skeletal muscle toxicity	
Grade 1	Recommendation: Maintain study treatment and dose level.
Grade 2 and Grade 3	Recommendation: Interrupt study treatment.
	Consider resuming study treatment without dose modification upon resolution to ≤ Grade 1 with appropriate management.
Grade 4	Mandatory: Permanently discontinue study treatment.
	In some cases, reintroduction of study treatment may be considered after discussion with the Novartis Medical Monitor and consultation with a rheumatologist.
Neurological toxicity	
Any neurological adverse events	
Grade 1	Recommendation: Maintain study treatment and dose level.
Grade 2 and above	Mandatory: Interrupt study treatment until evaluation by neurologist and discussion with Novartis Medical Monitor.
Skin and subcutaneous tissue disor	ders
Rash/CCI	
Grade 1	Recommendation: Maintain study treatment and dose level and treat the participant per institutional practice Consider initiating appropriate therapy for cutaneous toxicity (such as antihistamines, topical corticosteroids or low-dose systemic corticosteroids).
Grade 2	Recommendation: Consider interrupting study treatment and treat the participant per institutional practice initiate/intensify appropriate therapy for cutaneous toxicity (such as antihistamines, topical corticosteroids or low-dose systemic corticosteroids). If study treatment is interrupted, upon resolution to ≤

	Grade 1, resume study treatment at the same dose	
Grade 3, despite appropriate therapy for cutaneous toxicity	level. Recommendation: Interrupt study treatment until resolved to Grade ≤ 1 and treat the participant per	
	institutional practice then:	
	If resolved in ≤ 7 days, reduce 1 dose level.	
	If resolved in > 7 days (despite appropriate therapy for cutaneous toxicity), permanently discontinue study treatment.	
Grade 4, despite appropriate therapy for cutaneous toxicity	Mandatory: Permanently discontinue study treatment.	
Fatigue/ Asthenia (General disorders and administ	ration site conditions)	
Grade 1 and 2	Recommendation: Maintain study treatment and dose level.	
Grade 3	Recommendation: Interrupt study treatment until resolved to ≤ grade 1, then:	
	If resolved in ≤ 7 days, maintain dose level.	
	If resolved in > 7 days, reduce 1 dose level.	
Ocular (uveitis, eye pain, blurred vision)		
Grade 1	Recommendation: Maintain study treatment and dose level. Ophthalmology consultation is required within 72 hours, except for dry eye.	
Grade 2	Recommendation: Interrupt study treatment.	
	Urgent ophthalmology consultation.	
	Upon resolution to ≤ Grade 1 in < 14 days, may consider reintroducing study treatment without dose reduction after discussion with the Novartis medical Monitor and consultation with ophthalmology.	
	Upon resolution to ≤ Grade 1 in ≥ 14 days, study treatment may be reintroduced at 1 lower dose level after discussion with the Novartis Medical Monitor and consultation with ophthalmology.	
Grade 3 and Grade 4	Mandatory: Permanently discontinue study treatment. Urgent ophthalmology consultation.	
Retinal vein occlusion or Retinal detachment		
Any Grade	Mandatory: Permanently discontinue study treatment. Urgent ophthalmology consultation.	
Other adverse events		
Grade 1 and 2	Recommendation: Maintain study treatment and dose level.	
Grade 3	Recommendation: Interrupt study treatment until resolved to ≤ grade 1, then reduce 1 dose level.	
	Mandatory: Interrupt study treatment for ≥ grade 3 vomiting or grade 3 nausea only if the vomiting or nausea cannot be controlled with optimal anti-emetic therapy (as per local practice).	
Grade 4	Mandatory: Permanently discontinue study treatment.	

^a Common Toxicity Criteria for Adverse Events (CTCAE Version 5.0)

^b Core LFTs consist of ALT, AST, GGT, total bilirubin (fractionated [direct and indirect], if total bilirubin > 2.0 x ULN), and alkaline phosphatase (fractionated [quantification of isoforms], if alkaline phosphatase > 2.0 x ULN)

 $^{^{\}rm c}$ "Combined" defined as total bilirubin increase to the defined threshold concurrently with ALT/AST increase to the defined threshold

If combined elevations of AST or ALT and total bilirubin do not meet the defined thresholds, please follow the instructions for isolated elevation of total bilirubin and isolated elevation of AST/ALT, and take a conservative action based on the degree of the elevations (e.g., permanently discontinue treatment at the situation when omit dose is needed for one parameter and permanently discontinue treatment is required for another parameter). After all elevations resolve to the defined thresholds that allow treatment re-initiation, re-start the treatment either at the same dose or at one dose lower if meeting a criterion for dose reduction

^d "Cholestasis" defined as ALP elevation (> 2.0 × ULN and R value < 2) in participants without bone metastasis or elevation of ALP liver fraction in participants with bone metastasis

Note: The R value is calculated by dividing the ALT by the ALP, using multiples of the ULN for both values. It denotes whether the relative pattern of ALT and/or ALP elevation is due to cholestatic ($R \le 2$), hepatocellular ($R \ge 5$), or mixed (R > 2 and R > 5) liver injury

- * Note: If total bilirubin > 3.0 × ULN is due to the indirect (non-conjugated) component only, and hemolysis as the etiology has been ruled out as per institutional guidelines (e.g., review of peripheral blood smear and haptoglobin determination), then reduce 1 dose level and continue treatment at the discretion of the Investigator.
- **Note: A CT scan or other imaging study to assess the pancreas, liver, and gallbladder must be performed within 1 week of the first occurrence of any ≥ Grade 3 elevation of amylase and/or lipase. If asymptomatic Grade 2 elevations of lipase and/or amylase occur again at the reduced dose, participants will be permanently discontinued from study treatment.
- *** Note: Antidiarrheal medication is recommended at the first sign of abdominal cramping, loose stools, or overt diarrhea

**** Note: JDQ443 has shown CC . The Investigators should recommend the use of precautionary measures against CC . To the participants during treatment with JDQ443 CC .

Table 6-4 Dose reduction steps for JDQ443

Dose reduction*	Starting dose level 0	Dose level – 1	Dose level – 2
JDQ443	200 mg b.i.d.	100 mg b.i.d.	100 mg QD. (once a day)**

^{*}Dose reduction should be based on the worst toxicity demonstrated at the last dose.

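### Section 6.5.1 permits a lower-dose restart after 8 to 21 days off drug, without excepting the two Recommendation-headed rows of Table 6-3 (Grade 3 rash, Grade 2 ILD/pneumonitis) that say stop after 7 days

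*Protocol*

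**What the plan says.** Table 6-3 (Protocol, Section 6.5.1) sets actions by event and grade, each headed Recommendation or Mandatory.

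- **Grade 3 rash, Recommendation.** Interrupt until Grade 1 or better. If that takes 7 days or less, go down one dose level. Otherwise: "If resolved in > 7 days (despite appropriate therapy for cutaneous toxicity), permanently discontinue study treatment".
- **Grade 2 ILD/pneumonitis, Recommendation.** Interrupt during the work-up. A first occurrence that resolves in 7 days or less may restart one level lower, with daily oximetry for two weeks and a chest x-ray. Otherwise: "If symptoms fail to resolve within 7 days or recur after reintroduction of study treatment, permanently discontinue study treatment".

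The text of Section 6.5.1 has its own general rules for treatment-related toxicities, tiered by time.

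- **Resolved within 7 days.** Restart at the same or a lower dose at the investigator's discretion, "except for toxicities that require permanent treatment discontinuation (Table 6-3 and Table 6-4").
- **Longer interruptions.** For those of "more than 7 but not more than 21 days, study treatment may be resumed but only at a lower dose level". A participant already at the lowest level may stay there with sponsor approval. The sentence contains no exception.
- **Interruptions over 21 days.** Discontinue, with exceptions for clinical benefit: "The Investigator must discuss and receive approval from Novartis Global Medical Director or designee prior to continuing study treatment in this situation".

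The section also says that permanent discontinuation is mandatory for events so indicated in Tables 6-3 and 6-4.

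**The concern.** The exception for discontinuation toxicities is attached to the wrong tier for these two rows. Their slow-resolution stop instructions take effect only after day 7, so an exception on the within-7-days sentence cannot reach them. The next sentence, which covers the period when they do apply, permits a restart and has no exception.

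A site that works from the row stops the drug. A site that works from the section text restarts it at a lower dose, after a course for which the row advises against restarting. Following the text also removes the distinction that the rows draw at 7 days. A slow Grade 3 rash would be handled like a quick one. A slowly resolving Grade 2 pneumonitis could restart without the oximetry and x-ray that the row attaches to a quickly resolving one.

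In this window the text requires sponsor approval only for a participant already at the lowest dose level. At stake are the safety of re-exposed participants and uniform handling across sites.

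**Working it through.** The check is a comparison of texts. The plan states no figure to reproduce.

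**Step 1. Compare the instructions by time.**

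| Time | Grade 3 rash row | Grade 2 ILD/pneumonitis row | Section 6.5.1 text |
|---|---|---|---|
| 7 days or less | Down one level | First occurrence: may restart one level lower, with monitoring | Same or lower dose, discontinuation toxicities excepted |
| More than 7, up to 21 days | Stop (recommended) | Stop (recommended) | May restart, lower dose only, no exception |
| More than 21 days | Stop (recommended) | Stop (recommended) | Stop, unless the sponsor approves an exception |

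Only the middle line pairs a stop with a restart that has neither an exception nor, above the lowest level, a sponsor check.

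**Step 2. Check that the clocks can coincide.** The rows count time to resolution, whereas the text counts length of interruption. Both must exceed 7 days for the instructions to diverge. That is likely, because both rows tell the site to hold the drug. Example: a related Grade 3 rash, drug held from onset, back to Grade 1 on day 12. The row advises permanent discontinuation; the text permits restart at a lower dose. The window runs from day 8 to day 21, which is 21 − 8 + 1 = 14 possible day counts.

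**Step 3. Check whether other wording closes the gap.** The mandatory-discontinuation sentence covers rows headed Mandatory, such as Grade 4 rash and confirmed Grade 3 or 4 ILD. It does not clearly reach rows headed Recommendation. Section 7.1 requires discontinuation for an adverse event that requires it, but refers back to Section 6.5.1 for which events those are. Its general duty to stop for the participant's well-being, and the Section 8 instruction to discuss immediate safety concerns with the sponsor, help in practice. Neither says which text governs.

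**Step 4. Size the two outcomes.** From Table 6-4, the starting dose is 2 × 200 = 400 mg/day and one level lower is 2 × 100 = 200 mg/day, so 200/400 = 50%. For a participant at the starting dose the choice is 0 or 200 mg/day.

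**Step 5. Frequency.** No rate is given for Grade 3 rash or Grade 2 ILD/pneumonitis. Section 2.2.3.3.2 lists related events seen in at least 10% of 39 first-in-human patients, and neither rash nor ILD is listed. As single reported terms they therefore occurred in at most 3 of 39 patients at any grade (3/39 = 7.7%; 4/39 = 10.3% would be listed). This is only indicative: events can be split over several terms, the rash row also covers a redacted term, and the visible safety text is cut.

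**The case against.** The strongest reply is that nothing conflicts. The text gives a permission with a cap, the rows give event-specific advice not to use it, and both can stand. Section 6.5.1 says that the tables summarise the dose modifications and that reductions should follow the table steps, and for a slow Grade 3 rash the table offers no reduction step. Most investigators would probably follow the specific row. **Much of this stands:** there is no strict contradiction and no mandatory rule is breached. But no sentence says that the row prevails, and the one exception that would have said so sits on the neighbouring sentence.

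A reader might infer that every discontinuation in Table 6-3 is undercut. The documents do not support that, because Section 6.5.1 separately makes the Mandatory ones binding.

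A reader might also infer a general breakdown between table and text, since some rows are looser than the lower-dose cap. Examples are skeletal muscle Grade 2–3 ("Consider resuming study treatment without dose modification upon resolution to ≤ Grade 1 with appropriate management") and ocular Grade 2 ("Upon resolution to ≤ Grade 1 in < 14 days, may consider reintroducing study treatment without dose reduction"). Rows that depart in both directions fit equally well with the row governing and the text being the default, so they do not show that the order is unknowable. The LVEF row ("If LVEF has recovered to within 10%-point below baseline, restart study treatment at the same dose") is a weak example. Imaging is repeated after 3 weeks, so the interruption falls mostly under the rule for more than 21 days.

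**Conclusion.** The point holds, as a minor one. It covers two Recommendation-headed rows, one sentence, and interruptions of 8 to 21 days for treatment-related events. Within that window the protocol advises stopping in one place and permits a lower-dose restart in another, without saying which applies. The conclusion assumes that a row headed Recommendation is not one for which the tables indicate mandatory discontinuation, which is the natural reading of the two labels. If the sponsor intends those stops to be binding, the headings do not show it.

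A reader might infer an effect on the efficacy results. The documents do not support that. Discontinuation is handled by a treatment-policy strategy for the primary endpoint (Protocol Section 3.1, SAP Section 2.6.3), and no estimand definition, hypothesis test or error rate depends on this sentence. The number of participants affected cannot be derived. What is visible suggests that it would be small.

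**What to change.** In Section 6.5.1, add to the 7-to-21-day sentence only: *except where Table 6-3 calls for permanent discontinuation of study treatment, whether recommended or mandatory*. The closing words matter. Repeating the existing exception, which speaks of toxicities that require discontinuation, might again miss rows headed Recommendation.

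The clause should not be widened to say that Table 6-3 applies whenever it has an event-specific instruction. That would lift the lower-dose cap for many rows that allow the same dose, among them Grade 2 creatinine, Grade 2 diarrhea, endocrine events and skeletal muscle toxicity. The cap should stay unchanged for all rows other than the stop instructions.

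The cost is one clause in the next amendment, with no new procedure or data. The downside is slightly less discretion to restart after Grade 3 rash or Grade 2 ILD/pneumonitis.
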